#### email: [contact]

A subject becoming pregnant while on study drug will immediately be withdrawn from the study and ET study procedures will be performed. The subject or partner should be followed by the Investigator (or designee) until completion of the pregnancy. If the pregnancy ends for any reason before the anticipated date, the Investigator (or designee) should notify Covance or the Sponsor's Clinical Safety Representative. At the completion of the pregnancy, the Investigator (or designee) will document the outcome of the pregnancy. If the outcome of the pregnancy meets the criteria for immediate classification as an SAE (ie, postpartum complication, spontaneous abortion, stillbirth, neonatal death, or congenital anomaly), the Investigator (or designee) should follow the procedures for reporting an SAE.

Male subjects will be instructed to notify the Investigator (or designee) immediately if they discover their sexual partner is pregnant. In this instance, the partner must provide written consent before pregnancy information can be collected. When a Clinical Research Unit (CRU) becomes aware that the female partner of a male subject is pregnant, they are to contact the Investigator (or designee) immediately (within 24 hours of the CRU staff becoming aware of the event) in addition to notifying Covance or the Sponsor's Clinical Safety Representative via email.

All pregnancies should be recorded on the AE electronic Case Report Form (as appropriate), in addition to completion of the required pregnancy forms. If the Investigator (or designee) suspects that a pregnancy was the result of an interaction between the study treatment and the

contraceptive method, in addition to the pregnancy the drug interaction should also be captured as a separate AE.

#### **Definition of Serious Adverse Events**

An SAE (by FDA definition) is any adverse drug experience occurring at any dose that results in any of the following outcomes:

- Death;
- A life-threatening adverse drug experience (ie, one that places the subject, in the view of the Investigator [or designee], at immediate risk of death);
- Inpatient hospitalization or prolongation of existing hospitalization;
- A persistent or significant disability/incapacity;
- A congenital anomaly/birth defect;
- An important medical event that may require medical or surgical intervention to prevent 1 of the above outcomes.

Important medical events that may not result in death, be life-threatening, or require hospitalization may be considered SAEs when, based on appropriate medical judgment, they may jeopardize the patient or subject and may require medical or surgical intervention to prevent 1 of the outcomes listed in this definition.

## Unexpected Adverse Drug Reaction

An AE or suspected adverse drug reaction is considered 'unexpected' if the event is not listed in the Reference Safety Information section of the IB or if it is not listed at the specificity or severity that has been observed for an unapproved IMP.

## Reporting

The FDA-reportable AEs are AEs that are associated with the use of the drug and represent events that are assessed as serious, related, and unexpected. The FDA-reportable AEs will be reported by the CRU to the Sponsor and the responsible IRB. Final determination of whether an event represents a SUSAR will be the responsibility of the Sponsor.

Within 24 hours of when an AE that is potentially FDA-reportable is first recognized or reported, and within 24 hours of any SAE (regardless of whether the event is assessed as related or unrelated to study drug) being first recognized or reported, Covance or the Sponsor's Clinical Safety Representative will be notified by the Investigator (or designee) in writing using the following email address:

#### email: [contact]

To report the SAE, the completed report form should be sent by email to Covance or the Sponsor's Clinical Safety Representative within 24 hours of awareness. Incoming reports are reviewed during normal business hours. Additional reporting instructions and the SAE Report Form are provided in the Study Manual.

The IRB will be notified of any FDA-reportable AE within the timeframe required by the IRB. The IRB Serious and Unexpected Adverse Experience Submission Form will be completed and submitted with the copy of the written confirmation or summary of the AE.

Protocol CONFIDENTIAL Protocol Reference: LOXO-BTK-20016 Covance Study: 8425120

# **Appendix 2: Clinical Laboratory Evaluations**

Clinical Chemistry Panel	Hematology Panel:	Other Tests:
(Fasted):	inclinatology I and:	Other rests.
Alanine aminotransferase (ALT)	Hematocrit	Hemoglobin A1c (HbA1c) b
Albumin	Hemoglobin	Thyroid-stimulating hormone
Alkaline phosphatase (ALP)	Mean corpuscular hemoglobin	(TSH) b
Amylase	Mean corpuscular hemoglobin	Estimated glomerular filtration
Aspartate aminotransferase	concentration	rate a,d
(AST)	Mean corpuscular volume	SARS-CoV-2 (COVID-19) test
Bilirubin (direct and total)	Platelet count	
Blood urea nitrogen	Red blood cell (RBC) count	Coagulation Parameters:
Calcium	RBC distribution width	Partial thromboplastin time
Chloride	White blood cell (WBC) count	Prothrombin time
Cholesterol	WBC differential (percent and	International normalized ratio
Creatine kinase	absolute):	
Creatinine	Basophils	Serology:b
Glucose	Eosinophils	
Iron	Lymphocytes	Human immunodeficiency virus
Lipase	Monocytes	(HIV) antibody
Magnesium	Neutrophils	Hepatitis B surface antigen
Phosphorus		(HBsAg)
Potassium		Hepatitis B virus (HBV) core
Sodium		antibody
Total protein		Hepatitis C virus (HCV)
Triglycerides		antibody
Uric acid		For Female Subjects only:
		Pregnancy test (serum
	Urinalysis:	qualitative, serum quantitative
	Bilirubin	may be used for confirmation if
		needed) c
	Color and appearance Glucose	Follicle-stimulating hormone
	Ketones	(post-menopausal female
		subjects only) b
	Leukocyte esterase Nitrite	
Urine Drug Screen:a	Occult blood	
Including, but not limited to the	pH and specific gravity	
following:	Protein	
Alcohol (ethanol)	Urobilinogen	
Amphetamines	Microscopic examination	
Barbiturates	including bacteria, casts,	
Benzodiazepines	crystals, epithelial cells, RBCs,	
Cannabinoids	and WBCs (if protein, leukocyte	
Cocaine (metabolite)	esterase, nitrite, or blood is	
Methadone	positive)	
Opiates		
Phencyclidine		
Cotinine		
	(Day -1) only	

a. Performed at Screening and Check-in (Day -1) only.

b. Performed at Screening only.

c. Performed at Screening, Check-in (Day -1), and Day 15/End of Treatment (EOT) or Early Termination (ET) only. d. Calculated using the Chronic Kidney Disease Epidemiology Collaboration (CKD-EPI) equation.

# **Appendix 3: Total Blood Volume**

The following blood volumes will be withdrawn for each subject.

Assessment	Approximate Blood Volume per Sample (mL)		Approximate Total Volume (mL)
Serology	8.0	1	8.0
Hemoglobin A1c	4.0	1	4.0
Repaglinide pharmacokinetic (PK)	4.0	50a	200.0
sampling LOXO-305 PK sampling	4.0	52ª	208.0
Clinical laboratory evaluations:			
Hematology	4.0	7	77.0
Clinical chemistry b	4.0	7	77.0
Coagulation parameters	3.0	7	
Serum pregnancy test (female subjects only)	4.0	3	12.0
Serum follicle-stimulating hormone (post-menopausal female subjects only)	4.0	1	4.0
Total:			313.0 mL

<sup>aAt PK sampling timepoints where multiple analytes (ie, repaglinide and LOXO-305) are assessed, a single blood sample will be taken for analysis (see Appendix 4).
b Thyroid stimulating hormone and eGFR will be assessed as part of the clinical chemistry sample.

If extra blood samples are required, the maximum blood volume to be withdrawn per subject will not exceed 450 mL.

# **Appendix 4: Schedule of Assessments**

			Period 1	Period 2											Clinic Discharge/ EOT/ET u	Follow-up Phone Call (EOS)			
Study Procedures a	Screening (Days -29 to -2)	(Day -1)	1	2	3	4	5	6	7	8	9	10	11	12	13	14	15	16	7 (± 2) days post EOT/ET w
Confined to the CRU		X	X	X	X	X	X	X	X	X	X	X	X	X	X	X	X	X	
Inclusion/Exclusion Criteria	X	X																	
Informed Consent	X																		
Demographics	X																		
Medical History	X	Xb																	
Height/Weight/BMI	Xc	Xc																	
eGFR	X	X																	
Physical Examination d		X																X	
12-lead ECG e	X	X	X	X				X						X				X	
Vital Sign Measurements f	$X^{g,h}$	$X^{g,h}$	$X^h$	X				X						X				$X^{g,h}$	
HDYF? Inquiryi	X	X	X	X	X	X	X	X	X	X	X	X	X	X	X	X	X	X	X
AEs/SAEs j	X	X	X	X	X	X	X	X	X	X	X	X	X	X	X	X	X	X	X
Repaglinide Dosing k			X											X					
LOXO-305 Dosing 				X	X	X	X	X	X	X	X	X	X	X					
CCI																			
Clinical Laboratory Evaluations o	X	X		X				X					X		X		X v	X v	
Hepatitis and HIV Screen	X																		
COVID-19 Test p	X	X																	
HbA1c Test	X																		
Drug Screen q	X	X																	
Prior and Concomitant Medications r	X	X	X	X	X	X	X	X	X	X	X	X	X	X	X	X	X	X	X
Serum Pregnancy Tests	X	X															X v	X v	
FSH Test t	X																		

Covance Study: 8425120 Protocol Reference: LOXO-BTK-20016

		Period 1														Clinic Discharge/ EOT/ET u	Follow-up Phone Call (EOS)	
Study Procedures a	Screening (Days -29 to -2)		2	3	4	5	6	7	8	9	10	11	12	13	14	15	16	7 (± 2) days post EOT/ET w
TSH Test	X																	

Abbreviations: AE = adverse event; BMI = body mass index; BP = blood pressure; COVID-19 = SARS-CoV-2; CRF = Case Report Form; CRU = Clinical Research Unit; ECG = electrocardiogram; eGFR= estimated glomerular filtration rate; EOS = End of Study; EOT = End of Treatment; ET = Early Termination; FSH = follicle-stimulating hormone; HbA1c = hemoglobin A1c; HDYF? = How Do You Feel?; HIV = human immunodeficiency virus; ICF = Informed Consent Form PK = pharmacokinetic; QD = once daily; SAE = serious adverse event; TSH = thyroid-stimulating hormone; UA = urinalysis.

- a. For details on study procedures, see Section 7.
- b. Interim medical history only.
- c. Height collected at Screening only, body mass index based on Screening height.
- d. A complete physical examination will be performed at Check-in (Day -1) and an abbreviated physical examination will be performed at EOT (Day 16) or ET.
- e. The 12-lead ECGs will be obtained at Screening and Check-in (Day -1), Day 1 (predose), Day 2 (predose, 2 hours after LOXO-305 dosing), Day 6 (predose and 2 hours after LOXO-305 dosing), Day 12 (predose, and 2 hours after LOXO-305 and repaglinide dosing), and EOT (Day 16, ie, 96 hours after LOXO-305 and repaglinide dosing on Day 12) or ET. When scheduled at the same time as blood draws, 12-lead ECGs should be carried out prior to and as close as possible to having blood drawn. The 12-lead ECGs will be collected after the subject has rested in the supine position for at least 10 minutes. The allowed sampling window for 12-lead ECGs is ± 30 minutes from the nominal timepoint for all postdose 12-lead ECGs and no less than 10 minutes prior to dosing for predose 12-lead ECGs.
- f. Vital sign measurements (supine blood pressure [BP] and pulse rate) will be obtained at Screening and Check-in (Day -1), Day 1 (predose), Day 2 (predose, 2 hours after LOXO-305 dosing), Day 6 (predose and 2 hours after LOXO-305 dosing), Day 12 (predose, and 2 hours after LOXO-305 and repaglinide dosing), and EOT (Day 16, ie, 96 hours after LOXO-305 and repaglinide dosing on Day 12) or ET. When scheduled at the same time as blood draws, vital sign measurements should be carried out prior to and as close as possible to having blood drawn. BP and pulse rate will be measured using the same arm for each reading after the subject has been supine for at least 5 minutes. The allowed sampling window for vital sign measurements is ±30 minutes from the nominal timepoint for all postdose vital sign measurements and no less than 10 minutes prior to dosing for predose vital sign measurements.
- g. Oral temperature and respiratory rate will be obtained at Screening and Check-in (Day -1), and EOT (Day 16) or ET.
- h. Oxygen saturation will be measured via pulse oximetry once at Screening, Check-in (Day -1), predose on Day 1, and EOT (Day 16) or ET. The allowed sampling window for predose oxygen saturation measurements is no less than 10 minutes prior to dosing.
- i. An HDYF? inquiry will be performed at Screening (after the ICF is signed), at Check-in (Day -1), at each postdose vital sign measurement, and at an appropriate time for all other days.
- j. AEs and SAEs will be collected beginning at informed consent. AEs will be recorded throughout the study (ie, from signing of the ICF until EOS, or until ET if the subject discontinues from the study and does not complete a follow-up phone call), either as subject medical history (if the event is reported as beginning prior to signing of the ICF or if the event occurs prior to study drug administration on Day 1 and is assessed as not related to study procedures by the Investigator [or designee]) or as AEs (if the event occurs after signing of the ICF but prior to study drug administration on Day 1 and is assessed by the Investigator [or designee]) as related to study procedures, or if the event occurs after study drug administration on Day 1 through EOT or ET regardless of relationship to study drug). From EOT or ET through EOS, only AEs assessed as related to study drug are to be recorded. All SAEs that develop from the time of ICF signing until EOS (or ET if the subject discontinues from the study and does not complete a follow-up phone call) are to be reported.
- k. On Day 1, repaglinide will be administered in the morning following a fast of 10 hours prior to dosing and subjects will receive a standardized light breakfast (examples of contents are detailed in Table 4) 15 minutes post-repaglinide dose. On Day 12, 200 mg LOXO-305 and 0.5 mg of repaglinide will be co-administered at the same time in the morning at the actual time of the Day 1 repaglinide dose (± 1 hour), following a fast of 10 hours prior to dosing and subjects will receive a standardized light breakfast (examples of contents are detailed in Table 4) 15 minutes post LOXO-305 and repaglinide dosing.

Covance Study: 8425120 Prot

1. On Days 2 through 11, oral doses of 200 mg LOXO-305 will be administered QD in the morning at the actual time of the Day 1 repaglinide dose (± 1 hour). On Days 2 through 11, subjects will be fasted for at least 2 hours predose and 1 hour postdose (with the exception of days where clinical laboratory evaluations are performed [Day 2, Day 6, and Day 11, where subjects are fasted for 8 hours predose and 1 hour postdose]). On Day 12, 200 mg LOXO-305 and 0.5 mg of repaglinide will be co-administered in the morning at the actual time of the Day 1 repaglinide dose (± 1 hour), following a fast of 10 hours prior to dosing and subjects will receive a standardized light breakfast (examples of contents are detailed in Table 4) 15 minutes post-LOXO-305 and repaglinide dosing.

to be fasted prior to clinical laboratory evaluations.

- p. Testing for COVID-19 will be conducted at a minimum at Screening and Check-in (Day -1). Testing for COVID-19 may also be conducted periodically during the subject's CRU confinement, at the discretion of the Investigator (or designee). Tests will be performed by rapid polymerase chain reaction or equivalent.
- q. Drugs of abuse urine test, including cotinine and alcohol. Results from the drugs of abuse tests will be used to determine subject eligibility per the inclusion/exclusion criteria.
- r. Prior and concomitant medication administration will be recorded beginning at informed consent. In addition, all Investigator-approved medications taken by a subject within 14 days, or 5 half lives (if known), whichever is longer, prior to Day 1 for prescription medications and over-the-counter medication, will be recorded on the subject's electronic CRF.
- s. Female subjects only.
- t. Post-menopausal female subjects only.
- u. The EOT is defined as when the subject is released from the CRU following completion of all assessments through Day 16 (EOT) or ET. The ET is defined as when the subject is released from the CRU if the subject terminates the study early. Vital sign measurements, ECG, and abbreviated physical examination results are to be available for review by the Investigator (or designee) prior to subject release from the CRU at the EOT visit. Clinical laboratory evaluation results for clinical chemistry, hematology, coagulation, and UA and serum pregnancy test results (female subjects only) are to be available for review by the Investigator (or designee) prior to subject release from the CRU at the EOT visit and prior to subject release from the CRU at the ET visit, if available.
- v. Clinical laboratory evaluations and serum pregnancy test (female subjects only) will be performed on the day prior to subject release from the CRU (Day 15) if the subject completes the study (EOT). Clinical laboratory evaluations and serum pregnancy test (female subjects only) will be performed on the day of subject release from the CRU if the subject terminates early (ET).
- w. To be conducted 7 days (± 2 days) following EOT (Day 16) or ET. The EOS is defined as when the subject is contacted by the CRU for a follow-up phone call 7 days (± 2 days) after the EOT visit or ET visit to determine if any SAE or study drug-related AE has occurred since the EOT or ET visit. All subjects who received LOXO-305 (including subjects who are terminated early) will receive a follow-up phone call.

z. Denotes predose sample collection only.

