#### 4.4. Exclusion Criteria

The following will exclude potential subjects from the study:

- 1. History or presence of any of the following, deemed clinically significant by the Investigator (or designee), and/or Sponsor:
  - a. liver disease
  - b. pancreatitis
  - c. peptic ulcer disease
  - d. intestinal malabsorption
  - e. cholecystectomy
  - f. gastric reduction surgery
  - g. history or presence of clinically significant cardiovascular disease:
    - i. Myocardial infarction or cerebrovascular thromboembolism within 6 months prior to Day 1
    - ii. Symptomatic angina pectoris within 6 months prior to Day 1
    - iii. New York Heart Association Class ≥ 2 congestive heart failure within 6 months prior to Day 1
    - iv. Congenital prolonged QT syndrome
    - v. Ventricular pre-excitation syndrome (Wolff-Parkinson White syndrome)
    - vi. Arrhythmia (excluding benign sinus arrhythmia) or history of arrhythmia requiring medical intervention
    - vii. Ventricular dysfunction or risk factors for Torsades de Pointes (eg, heart failure, cardiomyopathy, family history of Long QT Syndrome)
    - viii. Significant screening ECG abnormalities:
      - 1. left bundle-branch block
      - 2. second-degree atrioventricular (AV) block, type 2, or third-degree AV block
      - 3. QT interval corrected for heart rate using Fridericia's method (QTcF) is > 450 msec
      - 4. ECG findings deemed abnormal with clinical significance by the Investigator (or designee) at Screening, Check-in (Day -1), or prior to dosing on Day 1.

CONFIDENTIAL

Protocol Covance Study: 8425120 Protocol Reference: LOXO-BTK-20016

> Rechecks of out-of-range values for these ECG parameters that are not clinically significant (as determined by the Investigator [or designee]) will be permitted up to 2 times during Screening, Check-in (Day -1), and predose on Day 1 to confirm eligibility for the study if the values fall within the ranges stated above.

- 2. Subjects with out-of-range, at-rest (ie, supine for at least 5 minutes) vital sign measurements at Screening, Check-in (Day -1), or prior to dosing on Day 1, including:
  - a. oral body temperature > 37.5°C
  - b. pulse rate < 50 or > 99 beats per minute
  - c. systolic BP < 89 or > 139 mmHg
  - d. diastolic BP < 50 or > 89 mmHg
  - e. oxygen saturation < 95% (room air).

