Rechecks of out-of-range values for these parameters (oral body temperature, pulse rate, BP, and oxygen saturation) that are not clinically significant (as determined by the Investigator [or designee]) will be permitted up to 2 times during Screening, Check-in (Day -1), and predose on Day 1 to confirm eligibility for study participation if the values fall within the ranges stated above.

- 3. Clinically significant (as determined by the Investigator [or designee] and Sponsor) abnormal laboratory values (hematology panel, UA, clinical chemistry panel [fasted at least 8 hours], excluding those further defined in exclusion criteria #5, #6, #7, and #8 below) at Screening and/or Check-in (Day -1). Rechecks of clinically significant out-of-range clinical laboratory results (excluding those further defined in exclusion criteria #5, #6, #7, and #8 below) will be permitted up to 2 times during Screening and Check-in (Day -1) to confirm eligibility for study participation if the values fall within normal ranges or are stabilizing.
- 4. Clinically significant abnormality, as determined by the Investigator (or designee), from physical examination at Check-in (Day -1).
- 5. Abnormal liver function tests (LFTs), as defined by aspartate aminotransferase, alanine aminotransferase, and serum (total and direct) bilirubin, as well as amylase and lipase above the upper limit of the normal range at Screening or Check-in (Day -1). Rechecks of LFTs, amylase, and lipase above the upper limit of the normal range that are not clinically significant (as determined by the Investigator [or designee]) will be permitted up to 2 times during Screening and Check in (Day -1) to confirm eligibility for study participation if the values fall within normal ranges.
- 6. Any clinically significant deviations from normal ranges in creatine kinase unless approved by the Investigator (or designee) and Sponsor. Rechecks of out-of-range creatine kinase values that are not clinically significant (as determined by the Investigator [or designee]) will be permitted up to 2 times during Screening and Check in (Day -1) to confirm eligibility for study participation if the values are stable or trending down.
- 7. eGFR  $\leq$  80 mL/minute/1.73m^2 calculated using the Chronic Kidney Disease Epidemiology Collaboration (CKD-EPI) equation at Screening or Check-in (Day -1).

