#### 7.2. Safety and Tolerability Assessments

Safety evaluations may be repeated at the discretion of the Investigator (or designee) or Sponsor.

Every effort will be made to schedule and perform the procedures in accordance with the nominal time, giving considerations to appropriate posture conditions, practical restrictions, and any other procedures to be performed at the same timepoint. The order of priority for scheduling procedures around a timepoint is (in descending order of priority):

- dosing
- PK blood sampling
- vital sign measurements
- 12-lead ECGs
- blood and urine samples for clinical laboratory evaluations
- physical examination.

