#### 7.2.3. Vital Signs

Vital sign measurements (including oral temperature, respiratory rate, and supine BP, oxygen saturation and pulse rate) will be obtained at the timepoints specified in Appendix 4.

Blood pressure and pulse rate measurements should be performed using the same arm for each reading and measurements should be taken after the subject has been resting in the supine position for at least 5 minutes.

When vital sign measurements are scheduled at the same time as blood draws, the blood draws will be obtained at the scheduled timepoint, and the vital sign measurements will be obtained prior to and as close as possible to the scheduled blood draw.

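### Exclusion 2a applies an oral temperature limit before Day 1 dosing, but Appendix 4 schedules no temperature reading on Day 1

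*Protocol*

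**What the plan says.** **The criterion.** Protocol Section 4.4, exclusion 2, covers at-rest "vital sign measurements at Screening, Check-in (Day -1), or prior to dosing on Day 1, including" five items: (a) oral temperature above 37.5°C, (b) pulse rate, (c) systolic BP, (d) diastolic BP and (e) oxygen saturation. The paragraph that follows it begins "Rechecks of out-of-range values for these parameters (oral body temperature, pulse rate, BP, and oxygen saturation) that are not clinically significant" and says that these rechecks "will be permitted up to 2 times during Screening, Check-in (Day -1), and predose on Day 1 to confirm eligibility for study participation". Temperature is thus named explicitly in a rule that reaches to the Day 1 predose slot.

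**The timing.** Section 7.2.3 lists oral temperature among the vital signs and sets no timing of its own; it refers to Appendix 4 for that. In Appendix 4:

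- Footnote f limits the general vital-sign entry to supine blood pressure and pulse rate, and includes Day 1 predose.
- Footnote g covers temperature: "Oral temperature and respiratory rate will be obtained at Screening and Check-in (Day -1), and EOT (Day 16) or ET".
- Footnote h covers oxygen saturation: "Oxygen saturation will be measured via pulse oximetry once at Screening, Check-in (Day -1), predose on Day 1, and EOT (Day 16) or ET".
- In the vital-sign row, Screening, Check-in and Day 16 carry superscripts g and h. Day 1 carries h only.

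**Discretion.** Section 7.2 adds: "Safety evaluations may be repeated at the discretion of the Investigator (or designee) or Sponsor".

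**The concern.** An eligibility criterion can be applied at a timepoint only if the measurement it needs is available then. Section 4.4 makes a temperature above 37.5°C before Day 1 dosing a reason to exclude. The schedule that the site works from does not ask for a temperature at that time.

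A site following Appendix 4 exactly will have temperature on record at Screening and Check-in, and nothing for the third timepoint the criterion names. A subject who became febrile overnight could be dosed on Day 1 contrary to a written exclusion, and no source record would show it.

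There is some clinical context. Section 1.6 notes that repeated LOXO-305 dosing may lower white cell counts and describes precautions for the COVID-19 pandemic. COVID-19 testing is mandatory only at Screening and Check-in. Under footnote g, the next scheduled temperature after Check-in is at Day 16 or early termination. A Day 1 predose reading would be the only scheduled one in between.

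**Working it through.** The protocol gives no figure to reproduce here. The check is to set each exclusion 2 parameter against the three timepoints that the criterion names and see whether Appendix 4 schedules it.

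| Exclusion 2 item | Appendix 4 footnote | Screening | Check-in (Day -1) | Day 1 predose |
|---|---|---|---|---|
| 2a oral temperature | g | yes | yes | **no** |
| 2b pulse rate | f | yes | yes | yes |
| 2c systolic BP | f | yes | yes | yes |
| 2d diastolic BP | f | yes | yes | yes |
| 2e oxygen saturation | h | yes | yes | yes |

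Count, treating systolic and diastolic BP separately as the criterion does:

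- Checks implied: 5 items × 3 timepoints = 15.
- Scheduled: footnote f, 3 items × 3 = 9; footnote h, 1 × 3 = 3; footnote g, 1 × 2 = 2. Total 9 + 3 + 2 = 14.
- Not scheduled: 15 − 14 = 1, the Day 1 predose temperature. On Day 1 alone, 4 of 5 items are scheduled.

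Three further readings of the text were tested.

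1. *Could this be a fault of text extraction?* No. Two separate elements agree: the wording of footnote g omits Day 1, and the Day 1 cell lacks superscript g.
2. *Could the Day 1 entry include temperature without saying so?* No. Footnote f defines that entry as blood pressure and pulse rate, footnote h adds oxygen saturation, and temperature has its own footnote.
3. *Does another section schedule it?* No. Section 7.2.3 defers to Appendix 4, and Section 4.2 deals only with Check-in.

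The oxygen saturation schedule suggests an oversight. Saturation is measured predose on Day 1 but not on Days 2, 6 or 12, which is the pattern expected of a reading taken for the Day 1 eligibility check. Temperature has the same role in exclusion 2 but lacks the matching entry.

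**The case against.** The best case for leaving the text alone has four parts.

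- **The criterion does not itself order a measurement.** Exclusion 2 gives one list of timepoints, joined by an *or*, for five parameters. It can be read as saying when an out-of-range value disqualifies a subject. On that reading, if someone takes a Day 1 temperature the criterion works in full. This stands to a degree: the accurate statement is that no routine reading is scheduled, not that the criterion can never be applied.
- **A reading is permitted.** Rechecks are allowed predose on Day 1, and safety evaluations may be repeated at discretion (Sections 4.2 and 7.2). That is true, but neither provision requires a reading. A recheck presupposes an out-of-range value, and no initial Day 1 temperature is scheduled that could produce one.
- **Exposure is small.** Temperature is taken at Check-in the day before, a COVID-19 test is done then, subjects are confined from that point, and the investigator can exclude an ill subject under exclusions 19 and 29. This stands, and it is why the point ranks as minor. It does not show that a subject is afebrile on the morning of dosing.
- **The schedule may be right and the criterion wrong.** Footnote h adds Day 1 for oxygen saturation while the adjacent footnote g does not, and the inclusion/exclusion row in Appendix 4 is marked only at Screening and Check-in. A deliberate choice not to repeat temperature cannot be ruled out from the text. Removing Day 1 for temperature from exclusion 2 and its recheck paragraph would also reconcile the documents, but it would give up a stated safeguard to save one thermometer reading.

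**Conclusion.** The inconsistency is real. Section 4.4 applies the temperature limit before Day 1 dosing, and Appendix 4, to which Section 7.2.3 defers, schedules no temperature then. One of the 15 checks implied by exclusion 2 (1/15 = 6.7%) has no scheduled measurement. That share locates the gap but is not a measure of risk; the documents give no basis for estimating how often a subject would be febrile on Day 1 after a normal Check-in reading.

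The consequence is confined to eligibility documentation and a modest safety point on the first dosing day. The repaglinide AUC and Cmax comparison and the definitions of the PK and Safety Populations are unaffected. This is a minor correction, worth making because it costs almost nothing.

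The conclusion rests on reading exclusion 2 as intending all five parameters to be checked at all three timepoints. The recheck paragraph, which names both temperature and the Day 1 predose slot, supports that reading.

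**What to change.** In Appendix 4, add superscript g to the Day 1 vital-sign cell, and add to footnote g: *Oral temperature will also be obtained predose on Day 1.* Respiratory rate shares footnote g but is not an exclusion 2 parameter, so it does not need the extra timepoint.

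On paper the cost is one superscript and one sentence. In conduct it is one thermometer reading per subject in the predose vital-sign slot that already exists on Day 1: 1 × up to 16 subjects = up to 16 readings, before any rechecks, replacement subjects or subjects who fail the Day 1 check and are not dosed. No visit or blood draw is added.

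If the sponsor did intend to omit the Day 1 temperature, the alternative is to remove that timepoint for temperature from exclusion 2 and from its recheck paragraph. Adding the reading is preferable because it keeps the safeguard that the criterion already states.
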